9.4.1 Exposure to Partners during the Study

There is a significant risk of drug exposure through the ejaculate (which also applies to vasectomised males) that might be harmful to the sexual partners (both male and female), including pregnant partners of male subjects. Therefore, a condom should be used by all male subjects throughout the study and for 90 days after study discharge.

9.4.2 Sperm Donation

Male subjects should not donate sperm for the duration of the study and for at least 90 days after study discharge.

9.5 Pregnancy

Subjects will be instructed that if their partner become pregnant during the study this should be reported to the investigator. The investigator should also be notified of pregnancy occurring during the study but confirmed after completion of the study. In the event that a subject's partner is subsequently found to be pregnant after the subject is included in the study, then consent will be sought from the partner and, if granted, any pregnancy will be followed and the status of mother and/or child will be reported to the sponsor after delivery.

A pregnancy notification form and follow-up will be completed.

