6.3 Population Rationale

The European Medicines Agency (EMA) propose to include subjects in the age group 18 to 55 years with normal weight who are non smokers without a history of alcohol or drug abuse. The latter criteria are proposed to avoid interaction on drug metabolism and to avoid non compliance. In order to avoid any interaction with other medication, no co medication will be allowed.

As this is a Phase I study assessing the bioavailability, PK and safety of KD025, the most relevant population is healthy volunteers, as recommended by the FDA [27] and the EMA guidelines [28].

The purpose of this study is to show a difference between the applied conditions, and therefore it is an advantage to enrol a relatively homogeneous population and to minimise variability. Healthy male subjects, aged 18 to 55 years, will be therefore be enrolled.

Formal rat and rabbit embryo-foetal developmental toxicology studies with KD025 demonstrated potential for embryo-foetal toxicity and/or malformations at clinically relevant exposures. Therefore subjects with pregnant partners will be excluded from this study.

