10.3.6 Follow-up

A follow-up phone visit will take place 3 to 5 days after final discharge to ensure the ongoing wellbeing of the subjects. If a subject reports any AEs which can present a cause for concern, they will be required to attend the clinic for a further follow-up assessment (as an unscheduled visit). Completion of the last follow-up visit (including any unscheduled) will be considered the end of the study.

11 Dosing of Subjects

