18.5 Declaration of the End of the Study

The definition of the end of the study is defined as the last visit of the last subject (eg follow-up assessment). Any changes to this definition will be notified as a substantial amendment (see Section 17.1).

The EC and MHRA should be notified in writing of the conclusion of the study within 90 days of the end of the study, or within 15 days if the study is terminated early, clearly explaining the reasons for the termination.

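### Subjects are told to report a partner's pregnancy only if it occurs during the study, yet the protocol's embryo-foetal precautions run to 90 days after study discharge

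*Protocol*

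**What the plan says.** Section 9.5 of the protocol contains two notification sentences. The first is the instruction to subjects: "Subjects will be instructed that if their partner become pregnant during the study this should be reported to the investigator". The second extends it to late confirmation: "The investigator should also be notified of pregnancy occurring during the study but confirmed after completion of the study". A third sentence deals with what the site does next. It opens "In the event that a subject's partner is subsequently found to be pregnant after the subject is included in the study" and goes on to partner consent, follow-up of the pregnancy and a report to the sponsor after delivery. It gives no end date. A notification form is also to be completed.

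Section 10.3.6 fixes the last planned contact: "A follow-up phone visit will take place 3 to 5 days after final discharge to ensure the ongoing wellbeing of the subjects". It then states: "Completion of the last follow-up visit (including any unscheduled) will be considered the end of the study". Section 14.3 stops adverse event recording at the same visit, which it describes as discharge from the study. Section 18.5 sets the end of the study at trial level as the last visit of the last subject.

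The precautions run longer. Section 9.4 requires a condom plus effective contraception from consent until 90 days after study discharge, for subjects with a partner of child-bearing potential. Section 9.4.1 says that "a condom should be used by all male subjects throughout the study and for 90 days after study discharge". Section 9.4.2 bans sperm donation for at least the same period. Section 9.4.1 bases its rule on drug exposure through the ejaculate. Section 6.3 reports that rat and rabbit studies "demonstrated potential for embryo-foetal toxicity and/or malformations at clinically relevant exposures".

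**The concern.** The protocol treats the 90 days after study discharge as a period in which conception should be prevented, but the instruction to report a conception does not cover most of it. A contraceptive failure some weeks after discharge is the event that the precautions are meant to prevent. Followed as written, section 9.5 gives the subject no reason to tell the site about it, and no later contact is scheduled at which the site would ask.

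What is at stake is participant protection and safety information. In a small healthy-volunteer study of a compound with a stated embryo-foetal signal, a pregnancy in this window would be a rare human observation, and it could go unrecorded simply because nobody was asked to mention it.

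**Working it through.** The plan gives no figure of its own for this point. The check compares where two windows end.

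**Inputs**
- Start of precautions: informed consent (9.4).
- End of precautions: 90 days after study discharge (9.4, 9.4.1, 9.4.2).
- End of the notification duty for one subject: the follow-up contact, 3 to 5 days after final discharge (9.5 with 10.3.6), later if an unscheduled visit is needed.
- Meaning of study discharge: not defined. It could be the final discharge from the clinic, or the discharge at the follow-up visit described in 14.3.

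**Formula.** Gap = end of precautions minus end of notification duty.

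| Reading of study discharge | Calculation | Gap | Share of the 90 days |
|---|---|---|---|
| Final clinic discharge, follow-up on day 5 | 90 − 5 | 85 days | 85/90 = 94.4% |
| Final clinic discharge, follow-up on day 3 | 90 − 3 | 87 days | 87/90 = 96.7% |
| Discharge at the follow-up visit | 90 − 0 | 90 days | 100% |

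The gap is therefore 85 to 90 days, or about 12 to 13 weeks (85/7 = 12.1; 90/7 = 12.9).

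**Effect of the trial-level definition.** If *during the study* is read through section 18.5, the duty lasts until the last subject's last visit. For a subject who finishes early, the gap shrinks by the time between his own last visit and that date, and could disappear. For the last subjects to finish, the two dates coincide and the gap stays at 85 to 90 days. The documents give no dates from which to work out how many subjects fall in between.

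**Who does what.** Of the three relevant sentences in 9.5, the first places a duty on the subject and the second says that the investigator should be notified. Both are limited to pregnancies occurring during the study. The third has no end date, but it starts from a pregnancy that has already been found.

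**The case against.** Several objections have force.

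- **Follow-up is not ruled out.** A reader might infer that the site would never seek consent, follow a later pregnancy or report its outcome. The documents do not support that. The third sentence of 9.5 starts at inclusion, has no end date, and can be read to require all three steps for any later pregnancy that comes to light.
- **Other reporting routes exist.** A reader might also infer that nothing else could bring a post-study case to the sponsor. Section 14.4.1 counts a congenital anomaly as serious, section 16.1 lists serious events after completion that the sponsor considers SUSARs among those that may need expedited reporting, and the 24-hour rule in 16.3.1 runs from awareness with no end date. These routes are real, but each depends on somebody learning of the event.
- **The gap may not affect everyone.** It is tempting to say that every dosed subject loses 85 days or more. Section 18.5 may shorten the gap for early subjects. Not every subject has a partner of child-bearing potential. The maxima of 44 and 42 dosed subjects are ceilings, and the two parts may share subjects (exclusion criterion 1 in 9.3).
- **Days are not risk.** Section 5.3.2 gives a half-life of typically 4 to 8 h, with a few longer values. In Part 2 the last KD025 dose is 12 h after the morning dose and discharge is at 48 h, so the earliest follow-up is 36 + 72 = 108 h after that dose, or 108/8 = 13.5 half-lives at 8 h. The percentages above are shares of calendar time only, and a precautionary margin need not equal a reporting window. This stands as a limit on the size of the concern. But the protocol chose 90 days for three separate precautions and gives no reason for a shorter notification duty.
- **Subject information was not available.** The participant information sheet and the pregnancy notification form may say more than section 9.5 does.

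None of these supplies an explicit instruction to subjects for the post-study part of the window.

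**Conclusion.** The point holds as a gap in the instruction to subjects. On the subject-level reading of the end of study, about 85 to 90 days carry precautions without an explicit duty to notify. On the trial-level reading, the gap is smaller or absent for early subjects and unchanged for the last ones, so the duty would depend on the order in which subjects finish, which a subject cannot know.

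The conclusion rests on three assumptions: that *during the study* limits both notification sentences, that no scheduled contact follows the 3 to 5 day call, and that the subject information does not extend the duty. It does not show that later pregnancies would go without follow-up once known, that no other reporting route exists, or that every subject is affected. The documents allow no estimate of how many pregnancies might be missed; the number is probably very small.

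This is a worthwhile safety correction at low cost. It has no effect on the PK analysis, the sample size or the power.

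**What to change.** Reconcile section 9.5 with sections 9.4 to 9.4.2:

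1. Keep the present start of the notification duty, and in any case no later than the contraception window, which opens at consent. Starting it at first dose would create a new mismatch.
2. Extend the end of the duty to 90 days after study discharge in both notification sentences.
3. Define study discharge once, as either final clinic discharge or the follow-up visit, and use that meaning throughout 9.4 to 9.5.
4. State that the existing partner-consent, notification-form and outcome follow-up steps apply to any pregnancy in that window.
5. Tell subjects at discharge, alongside the 90-day contraception instruction, and make sure the subject information matches.

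The cost is a few lines in section 9.5, one definition and a matching line for subjects. If the information sheet changes through a substantial amendment, section 17.1 requires currently enrolled subjects to be re-consented. No visit, sample or analysis is added. The small downside is that the site remains a reporting contact for about 12 more weeks.

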9.6 Additional Study Restrictions

The following additional restrictions will be in place for the duration of the study:

- Subjects must abstain from alcohol during the 24 h prior to screening and the 24 h
 prior to admission in Period 1, and 24 h prior to commencing NIMP treatment in Part 1
 Periods 2 to 4 and Part 2 Period 2, until discharge for each treatment period
- Subjects must not drink liquids or eat food containing grapefruit or cranberry from 24 h prior to admission in Period 1, and 24 h prior to commencing NIMP treatment in Part 1 Periods 2 to 4 and Part 2 Period 2, until discharge for each treatment period
- 3. Subjects must not drink liquids or eat food containing caffeine or other xanthines from 24 h prior to admission until discharge for each treatment period

- 4. Subjects should refrain from eating food containing poppy seeds for 48 h prior to screening and for 24 h prior to admission until discharge for each treatment period
- 5. Subjects must not take part in any unaccustomed or strenuous exercise from the 72 h before the screening visit and then from 24 h prior to admission until discharge for each treatment period.

10 Study Procedures

Study procedures will be performed as detailed in the study schedule of assessments in Appendix 2 and Appendix 3, and in accordance with Quotient Sciences standard operating procedures unless otherwise stated in this protocol.

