6.1 Study Rationale

Preclinical data indicates that CYP3A4 plays a predominant role in the metabolism of KD025; therefore, drug-drug interactions will be investigated in this study to determine whether co-administration of KD025 with inhibitors or inducers of CYP3A4 results in altered exposure of KD025 and/or KD025m1 and KD025m2. In the present study, itraconazole and rifampicin will be used because they are classed as a strong inhibitor and inducer of CYP3A4, respectively.

In addition, the solubility of KD025 is pH dependent ie, it is 100 μ g/mL at pH 2.7, ~4 μ g/mL at pH 6.5 and ~3 μ g/mL at pH 7.4. Thus, the impact of a proton pump inhibitor (PPI), on the exposure of KD025 will also be assessed. Rabeprazole, a recognised PPI, suppresses the secretion of gastric acid by noncompetitive blockade of the H+/K+-adenosine triphosphatase at the secretory surface of the gastric parietal cells and raises the intra-gastric pH above 3.0. As rabeprazole increases pH, co-administration of rabeprazole with KD025 could result in a decrease in exposure of KD025.

Preliminary results from Part 1 (n=21) show that the exposure of KD025 is decreased (by approximately 80%) in subjects when taking rabeprazole (20 mg BID). Part 2 of the study has been designed to assess the impact of omeprazole (20 mg QD) on KD025 exposure. Omeprazole is a PPI widely used in clinical settings for the treatment of gastro-esophageal reflux disease, and to manage upper GI involvement in patients with cGVHD and IPF. Omeprazole has a weaker anti-secretory effect on gastric acid than rabeprazole [14]. Co-administration of omeprazole with KD025 could result in a smaller decrease in exposure of KD025 than observed with rabeprazole. Therefore, omeprazole will allow assessment of a weaker PPI interaction with KD025.

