8.1 Study Plan

This is a single centre, non-randomised, open label, two-part study.

8.1.1 Study Plan Part 1

Part 1 is a single centre, non-randomised, 4-period sequential dose assessment in healthy male subjects. In each period, subjects will receive a single dose of IMP, KD025 Tablet, in the fed state. Additionally, in order to assess the effects of inhibition and induction of CYP3A4 and the elevation of gastric pH on KD025 exposure, subjects will receive multiple doses of NIMP in Periods 2 to 4; a strong CYP3A4 inhibitor, itraconazole, in Period 2; a PPI, rabeprazole, in Period 3; and a strong CYP3A4 inducer, rifampicin, in Period 4:

Period	IMP/NIMP Dose
1	KD025 200 mg QD
2	itraconazole 200 mg QD for 7 days
	KD025 200 mg QD + itraconazole 200 mg QD on 8th day
	itraconazole 200 mg QD on 9 th day
3	rabeprazole 20 mg BID for 3 days
	KD025 200 mg QD + rabeprazole 20 mg QD on 4 th day
4	rifampicin 600 mg QD for 9 days
	KD025 200 mg QD on 10 th day

QD: once daily; BID: twice daily; details of the IMP and NIMPs are provided in Section 5.2.

It is planned to enrol 40 subjects to ensure there are 34 evaluable subjects; defined as those subjects who have sufficient PK data to assess the primary objective of Part 1 of the study.

All subjects will undergo preliminary screening procedures to determine their eligibility for Part 1 of the study at the screening visit (Day -28 to Day -2 of Period 1). For each period, subjects will be admitted to the clinic on the day prior to IMP administration (Day -1) for confirmation of eligibility and baseline procedures; morning admission for Periods 1, 2 and 4; evening admission for Period 3.

Prior to being admitted to the clinic in Periods 2 to 4, subjects will take multiple doses of the following NIMPs; itraconazole on Day 3 (Period 1; or Day -7 of Period 2 if washout period is extended) and continuing from Day -6 to -1 (Period 2); rabeprazole from Day -3 to -1 (Period 3); rifampicin from Day -9 to -1 (Period 4). Outpatient visits will take place on the mornings of Day -3 of Period 3 and Day -9 of Period 4, when the subjects will receive their morning dose of rabeprazole and rifampicin, respectively, and will be given sufficient supplies for home dosing. Subjects will also attend for an additional outpatient visit on the morning of Day -5 of Period 4 to receive their morning dose of rifampicin in the clinic, and will be given sufficient supplies for the remainder of the dosing period.

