10.2 Admission and Pre-dose Procedures

The identity of the subjects will be confirmed at admission and pre-dose.

In addition, the ongoing eligibility of subjects will be re-assessed at admission/pre-dose, as described in Sections 9.2 and 9.3.

Reserve subjects for the first dose occasion, in any group, will not require admission procedures to be repeated, if dosing is within 2 days.

Part 1: subjects will be admitted to the clinical unit on the morning before IMP administration (Day -1) for Periods 1, 2 and 4, and on the evening before IMP administration (Day -1) for Period 3.

Part 2: subjects will be admitted to the clinical unit on the evening before IMP administration (Day -1) for both periods.

The admission and pre-dose procedures are presented in Appendix 2 and Appendix 3

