11.4 Prior and Concomitant Medications

No medication will be permitted from 14 days before IMP administration until the follow-up visit except 4 g per day paracetamol and those deemed necessary by the investigator to treat AEs (see also Section 9.3). Any medications used will be recorded.

Emergency equipment and drugs will be available within the clinical unit as per current standard procedures. In the unlikely event that they are required, their use will be documented.

12 Assessment of Efficacy

Not applicable for this Phase I study.

13 Assessment of Pharmacokinetics and Pharmacodynamics

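### The grapefruit and cranberry ban starts 36 to 48 h before KD025 in the reference period but at least 4 to 10 days before it in the test periods, an avoidable asymmetry that could lower the ratios

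*Protocol*

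**What the plan says.** Protocol 9.6 item 2 sets two different starting points for the grapefruit and cranberry ban. For the reference period: "Subjects must not drink liquids or eat food containing grapefruit or cranberry from 24 h prior to admission in Period 1". For the test periods: "24 h prior to commencing NIMP treatment in Part 1 Periods 2 to 4 and Part 2 Period 2". In every period it ends at discharge.

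Admission is on Day -1. In Part 1, under section 10.2, "subjects will be admitted to the clinical unit on the morning before IMP administration (Day -1) for Periods 1, 2 and 4"; in Part 2, "subjects will be admitted to the clinical unit on the evening before IMP administration (Day -1) for both periods". The interacting drugs start well before KD025. Section 8.1 gives "itraconazole on Day 3 (Period 1; or Day -7 of Period 2 if washout period is extended", then rabeprazole from Day -3 and rifampicin from Day -9; section 11.1.2 gives omeprazole from Day -3.

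The alcohol rule in 9.6 has the same two-way start. The caffeine, poppy-seed and exercise rules start 24 h before admission in every period. The medication rule in 11.4 is tied to KD025 itself: "No medication will be permitted from 14 days before IMP administration until the follow-up visit".

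On metabolism, section 6.1 states: "Preclinical data indicates that CYP3A4 plays a predominant role in the metabolism of KD025". Section 5.3.1 bases this on human liver microsomes and adds that other routes may contribute. Neither document gives a size or duration for a grapefruit effect, or comments on the unequal lead times.

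**The concern.** Period 1 is the denominator of all four comparisons, and it has the shortest dietary lead before KD025 in both parts. A subject who has grapefruit three days before KD025 complies with 9.6 in Period 1 but would breach it in any test period. Because that intake is allowed, it is not a protocol deviation, so the deviation criterion in SAP 6.2 would not remove the profile. Neither document plans a record of intake that could support a sensitivity analysis.

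The model cannot help. Protocol 15.4 and SAP 9.2.4 fit treatment as fixed and subject as random, everyone follows the same order, and the footnote to mock Table 14.2.1.2.4 itself equates treatment with period.

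If an exposure-raising effect of grapefruit outlasted 36 to 48 h, the reference would be inflated. An itraconazole increase would be understated, and a rifampicin or proton pump inhibitor decrease overstated. Part 2 is the most exposed comparison, because section 6.1 anticipates a possibly smaller decrease with omeprazole and the result is judged against a 70.00% lower limit.

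**Working it through.** **Lead time before KD025** (there is no Day 0, so Day -k is k days before Day 1)

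| Period | Start of ban | Lead before KD025 |
|---|---|---|
| Part 1 Period 1 (reference) | 24 h before morning admission, itself about 24 h before KD025 | 24 + 24 = 48 h |
| Part 2 Period 1 (reference) | 24 h before evening admission, itself about 12 h before KD025 | 24 + 12 = 36 h |
| Itraconazole | 24 h before Day -7 | 7 + 1 = 8 days |
| Rabeprazole | 24 h before Day -3 | 3 + 1 = 4 days |
| Rifampicin | 24 h before Day -9 | 9 + 1 = 10 days |
| Omeprazole | 24 h before Day -3 | 3 + 1 = 4 days |

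With the minimum washout, itraconazole and omeprazole start on Day 3 of Period 1, so the ban runs on without a break from Period 1. The lead is then 2 + 2 + 7 = 11 days for itraconazole and 1.5 + 2 + 3 = 6.5 days for omeprazole.

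**The plan's sample size, reproduced.** Inputs from protocol 15.1: CVw 50% for Cmax, limits 70.00% to 143.00%, two one-sided tests at 0.05, true ratio 0.95 to 1.05, 80% power. The log-scale SD is sqrt(ln(1 + 0.5²)) = 0.472, and the standard error with n = 34 is 0.472 × sqrt(2/34) = 0.115. Exact power for the paired comparison (33 degrees of freedom) is 0.801 at a ratio of 0.95 and 0.806 at 1.05, and 34 is the smallest n that reaches 80% at either. The sample size stands and is not affected by this point.

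**What a given inflation would do (assumption).** If residual grapefruit raised the average reference exposure by r, each ratio would be divided by (1 + r). The documents give no value for r. Power below is for a single Cmax test with n = 34 and CVw 50%.

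| r | 0.95 becomes (power) | 1.00 becomes (power) | 1.05 becomes (power) | 0.20 becomes |
|---|---|---|---|---|
| 0% | 0.950 (0.80) | 1.000 (0.84) | 1.050 (0.81) | 0.200 |
| 5% | 0.905 (0.70) | 0.952 (0.80) | 1.000 (0.84) | 0.190 |
| 10% | 0.864 (0.56) | 0.909 (0.71) | 0.955 (0.81) | 0.182 |
| 20% | 0.792 (0.28) | 0.833 (0.44) | 0.875 (0.60) | 0.167 |

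The last column is the preliminary rabeprazole result in section 6.1, a decrease of about 80%.

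Only subjects who take grapefruit in the gap contribute to r. If a fraction f does so and each has reference exposure raised by a proportion q, the ratio is multiplied by (1 + q)^-f. This gives 0.995 for f 5%, q 10%; 0.982 for f 10%, q 20%; and 0.949 for f 20%, q 30%. The last corresponds to an average r of 1/0.949 - 1 = 5.4%. All of these values are assumed.

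**The case against.** The strongest objection is that the bias needs facts the documents do not contain: intake in the gap, an effect of grapefruit or cranberry on KD025 exposure, and persistence of that effect beyond 36 to 48 h. If the effect has gone by then, the bias is zero. If it lasts more than 4 days, the rabeprazole period is not fully protected either, since intake five days before KD025 can be allowed there. This stands, and it limits the point to a possible bias.

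A reader might infer that the ratios can only be biased downwards, or that inhibition in the gut wall is at work. The documents support neither. Section 5.3.1 reports first-pass metabolism in the species studied and, separately, CYP3A4 predominance in human liver microsomes; it does not mention gut CYP3A4.

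The wording of 9.6 also fits one simple rule: start 24 h before each period's first study activity. Relative to the first study drug, Period 1 then has the longer lead (36 to 48 h against 24 h). That may explain the asymmetry, but it does not remove it from the KD025 comparison. Likewise, the 14-day rule in 11.4 covers medication rather than diet.

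Nor would absence of an effect always be harder to conclude. At a true ratio of 1.05, power rises from 0.81 to 0.84 with 5% inflation. The rabeprazole ratio of about 0.20 would become about 0.18 at 10% inflation, which leaves the conclusion as it is.

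**Conclusion.** The asymmetry is real, unexplained and avoidable: about 2 days (Part 1) or 1.5 days (Part 2) in the reference, against at least 4, 8 and 10 days in Part 1 and at least 4 in Part 2. The design and model cannot separate it from treatment. It could lower the test/reference ratios if grapefruit raises KD025 exposure for longer than 36 to 48 h. Whether it does so is not in the documents, so the bias may be zero and cannot be quantified. It is probably small, since only subjects with intake in the gap contribute. The power figures show sensitivity to assumed inflations and are not an estimated loss. The comparison most worth protecting is omeprazole against the 70.00% limit. This is a cheap improvement and not a defect that undermines the study.

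**What to change.** In protocol 9.6 item 2, define the ban relative to KD025 dosing, with one common lead time per part, so that Period 1 is held to at least the lead required in the test periods it is compared with. The longest lead that 9.6 itself requires is 10 days in Part 1 and 4 days in Part 2; covering the run-on with minimum washout as well would take 11 and 6.5 days. If the sponsor prefers the present timing, the protocol should justify it.

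Exactly equal runs of abstinence are not attainable with minimum washout. If the Period 1 lead is L days, Period 2 inherits L + 2 + 7 = L + 9 days in Part 1 and L + 2 + 3 = L + 5 in Part 2. The aim is a common minimum that is long enough.

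Apply the change to Part 2 and to any Part 1 subjects not yet dosed. Ask about intake at the Period 1 admission, and record breaches as protocol deviations (protocol 17.2; listed under SAP 7.2). Section 6.1 already reports preliminary results for 21 Part 1 subjects; for subjects already dosed, acknowledge the unequal lead times as a limitation in the report.

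The cost is one sentence in 9.6 and the matching line in the participant information sheet. At the leads above, Part 2 subjects would have 4 - 1.5 = 2.5 more days of restriction before Period 1. Part 1 subjects would have 10 - 2 = 8 more before Period 1 and, with a common rule, 10 - 4 = 6 more before Period 3. Subjects screened closer to dosing than the lead time would need the instruction at booking.
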